A Comparison of McGrath[®] MAC versus C-MAC[®] Videolaryngoscopes in Morbidly Obese Patients Undergoing Bariatric Surgery: A Randomized, Controlled Clinical Trial

*[name], Asst. [name] of Anesthesiology and Reanimation, Inonu University Medical Faculty, Malatya, Turkey

[name], Asst. [name] of Anesthesiology and Reanimation, Inonu University Medical Faculty, Malatya, Turkey

[name], Asst. [name] of Anesthesiology and Reanimation, Inonu University Medical Faculty, Malatya, Turkey

Address all correspondence to:

[name], Asst. [name] of Anesthesiology and Reanimation, Inonu University Medical Faculty, Malatya, Turkey

Mail: [contact]

[contact]

[contact]

A short title: McGrath vs C-MAC in Morbidly Obese Patients

Conflict of Interest:

The authors declare that they have no conflict of interest.

Funding Information:

None

Study Protocol

Protocol: This study was approved by the Local Ethics Committee. We conducted a prospective, randomized, controlled clinical study with 80 morbidly obese adult patients undergoing bariatric surgery from 8 September to 20 October 2018 at a university hospital. This study was prepared in accordance with the Consolidated Standards of Reporting Trials [9].

Study Participants: Our study participants (n = 80) were morbidly obese patients with American Society of Anesthesiology (ASA) scores of III who were aged 18–65 years old, had a BMI \geq 40 kg/m2, and were presenting for bariatric surgery at our hospital. All surgery patients meeting these criteria during the study period were interviewed before surgery to obtain written informed consent to participate in the study. Patients who were aged under 18 - over 65 years old, pregnant or who had a BMI \leq 40 kg/m2, an allergy to anesthetic drugs, uncontrolled cerebrovascular disease, or drug and alcohol addiction were excluded, as were all patients who refused written informed consent.

Preoperative Procedures: Preanesthetic evaluations were performed on all patients one day before surgery. Age, gender, height, weight, BMI, ideal body weight (IBW), ASA physical status, and type of surgery were recorded. On the day of surgery, patients were taken to the operating room without premedication. Standard monitoring procedures were used, including heart rate (HR), noninvasive blood pressure (NIBP), electrocardiogram (ECG), peripheral oxygen saturation (SpO2), mean arterial pressure (MAP), and body temperature monitoring by esophageal probe.

General Anesthesia Protocol: A standardized general anesthesia protocol was administered to all patients. After preoxygenation (100% 4 L/min O2 for 3 min), patients were induced with propofol (1–2 mg/kg), rocuronium (0.8 mg/kg), and fentanyl (0.1 μ g/kg) via intravenous (IV) route at doses calculated according to IBWs. Mask ventilation and tracheal intubation using

either the McGrath MAC (blade size: 4) or C-MAC videolaryngoscopes (blade size: 4) were performed by an experienced anesthesiologist who had previously used both videolaryngoscopes successfully at least two years (more than 200 times). Also, tracheal intubations were performed by both videolaryngoscopes with the blade size 4 and using stylet in endotracheal tubes. End-tidal carbon dioxide (EtCO2) was continuously monitored after intubation. Tidal volume and ventilation rate were adjusted to maintain the EtCO2 partial pressure of arterial blood at 35–45 mmHg. Additional rocuronium was intermittently injected according to need based on Train of Four (TOF; Dräger AG, Lübeck, Germany) values. TOF responses were assessed by ulnar nerve stimulation and adductor muscle response. Additional fentanyl (0.1–0.2 μ g/kg) was titrated for analgesia, as needed, if HR and/or MAP increased by 20% above baseline during surgery. Anesthesia was maintained in both groups by desflurane inhalation in a 0.5 O2 oxygen-air mixture. Desflurane was discontinued with the beginning of skin sutures and fresh gas flow was changed to 4 L/min of oxygen. In patients who did not

experience complications during surgery, sugammadex (IV, 2–4 mg/kg; Bridion®, MSD, Greenville, USA) was then administrated to reverse residual muscle relaxation at the end of surgery.

Randomization: This study was planned as a randomized prospective study. Randomization was performed using MedCalc v. 16 statistical software for Windows (medcalc.com.tr). Eighty patients were randomly allocated to two groups: McGrath (n = 40) and C-MAC (n = 40) (**Figure 1.** Flow diagram). All patients received standard surgical procedures determined by the same team of surgeons with experience in gastroenterology surgery. Patient pneumoperitoneum pressure ranged from 10–12 mmHg and pneumoperitoneum levels ranged from 30–45 degrees. Surgical management of sleeve gastrectomy and gastric bypass surgeries was not changed in any way.

Postoperative Management: All patients were transferred to the post-anesthesia care unit (PACU) after surgery. Patients were then transferred to the general surgery intensive care unit when they achieved a score of 9 or higher on the Modified Aldrete score (range 0–12; scores of 9 and above indicate that the patient can be discharged from the PACU) [10]. In all patients, postoperative analgesia was achieved using appropriate IV doses of tramadol (0.5–1 mg/kg) and paracetamol (1 gr) at the time of beginning skin sutures [11].

Outcome Measures: Primary outcome measures were time to intubation and incidence for successful intubations. Time to intubation was defined as the time from when the anesthesiologist picked up the videolaryngoscope to when the anesthesiologist successfully placed the endotracheal tube through the vocal cords, which was assessed by the detection of meaningful EtCO2 levels using capnography. Also, time to intubation was recorded by another anesthesiologist, who accompanied to the study. The characteristics of each tracheal intubation were recorded perioperatively for both groups as secondary outcome measures, including the position requirements for successful intubations (the position at which successful intubation was achieved, neutral vs. sniffing position, i.e., head extension and neck flexion), Cormack Lehane grades (laryngeal view during endotracheal intubation with the videolaryngoscope on a grade of 1=full view of the glottis, 2=partial view of the glottis, 3=only epiglottis visible, 4=neither glottis nor epiglottis visible), glottic view (measured as percentage of glottic opening [POGO] scores), ease of intubation, patient hemodynamic responses and adverse events during intubation. POGO scores were measured on a scale of 1-4 (1 = 75-100% glottic opening; 2 =50-75%; 3 = 25-50%; 4 = 0-25%). Ease of intubation was defined on a grade of 1-3 (1 = noexternal manipulation of larynx was required; 2 = external manipulation of larynx was required; 3 = failed intubation on first two attempts). Incidence, attempts and position for successful intubation, Cormack Lehane grades, POGO scores, and ease of intubation were recorded by the anesthesiologist who performed the tracheal intubation.

Also demographic characteristics, comorbidities, and preoperative airway assessment, including each patient's Mallampati score (1–4), thyromental distance (cm), and mouth opening (cm), were recorded one day before surgery. HR, MAP, respiratory rate, and SpO2 were recorded at baseline before anesthesia (T₀), before intubation (T₁), 1 min after intubation (T₂), 2 min after intubation (T₃), 3 min after intubation (T₄), and 5 min after intubation (T₅). In addition, adverse events of tracheal intubation, including dental trauma, blood on blade, cuff burst, laryngospasm, bradycardia (HR < 65 beats/min), and hypoxemia (SpO2 < 90%), were recorded during the 15 min perioperative period. Hoarseness and sore throat were also recorded during the first 24 hours after surgery.

Sample Size: Statistical power analysis was performed based on a pilot study on 14 morbidly obese patients in our institution showing mean time to intubation of 45 ± 18.0 s [standard deviation (SD)] with the McGrath MAC. For power calculations (OpenEpi, Version 3), equal standard deviation for both groups was assumed. To show a difference of 12 s between the two groups and with an alpha of 0.05 and two tailed and a power of 80%, we calculated that a minimum of 36 patients per group should be included in this study. We ultimately included a total of 80 patients to allow for patient drop-out.

27.06.2018

Statistical Analysis:

Data were analyzed using the Statistical Package for the Social Sciences program (SPSS 22.0, IBM). The Kolmogorov-Smirnov normality test was used to test whether quantitative variables showed a normal distribution. As some patient preoperative and anesthetic characteristics were distributed abnormally, nonparametric statistics was used. Quantitative data are presented as mean or standard deviation and categorical data are shown as numbers or percentages. Continuous variables were compared between the groups using a Mann-Whitney U test. Categorical variables were summarized using frequencies and percentages, and were compared between the groups using a Chi-Square test or Fisher's exact test. A repeated measures ANOVA was used to compare hemodynamic data within each group, while an unpaired t-test was used for comparisons between the two groups. Results were evaluated at a 95% confidence interval at a significance level of p < 0.05.

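### Does the overlap of the two BMI criteria at exactly 40 kg/m² leave eligibility undefined?

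*Combined protocol and SAP*

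**What the plan says.** Study Participants gives the eligibility rules in one paragraph. Inclusion covers adults aged 18 to 65, ASA III, who "had a BMI \geq 40 kg/m2, and were presenting for bariatric surgery at our hospital". The exclusion sentence in the same paragraph lists, among other things, "pregnant or who had a BMI \leq 40 kg/m2, an allergy to anesthetic drugs". It also restates the age limits as exclusions: "Patients who were aged under 18 - over 65 years old".

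Preoperative Procedures says that BMI was noted at an evaluation one day before surgery: "Age, gender, height, weight, BMI, ideal body weight (IBW), ASA physical status, and type of surgery were recorded". It does not give the number of decimals or a rounding rule. No other section mentions a BMI threshold, and none comments on the overlap.

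**The concern.** An inclusion limit and its matching exclusion limit should be complements, and here they are not. The value 40 satisfies both, and it is the edge of the population named in the title. Taken literally, a screener faced with a BMI of 40 finds one sentence that admits the patient and another that removes the same patient.

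If that left the decision to discretion, two things could follow. The set of patients approached could not be reproduced from the text. A patient already randomized at BMI 40 could also be declared ineligible later and dropped. Exclusion after randomization is a recognised source of bias, and the Statistical Analysis section neither names an analysis population nor says what happens to a patient found ineligible after allocation. The worry is therefore reasonable on a first reading.

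**Working it through.** **1. The logic of the two rules.** Let I be the inclusion condition (BMI ≥ 40) and E the exclusion condition (BMI ≤ 40). A participant is eligible if I holds and E does not.

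| BMI | I | E | Eligible (I and not E) |
|---|---|---|---|
| 39.9 | no | yes | no |
| 40.0 | yes | yes | no |
| 40.1 | yes | no | yes |

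The two conditions overlap at one value and leave no gap. Read jointly they reduce to BMI > 40, so the text yields a decision for every patient. The fault is a mismatched pair, not an undecidable rule.

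**2. Comparison with the age limits.** Inclusion is 18 to 65; exclusion is below 18 or above 65. No age satisfies both and none satisfies neither. The same paragraph therefore handles its other numerical limit correctly, which points to a drafting slip in the BMI pair. It does not show which of the two BMI signs is the slip.

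**3. Does BMI enter the sample size?** The Sample Size section bases it on a pilot "showing mean time to intubation of 45 ± 18.0 s" and aims "To show a difference of 12 s between the two groups and with an alpha of 0.05 and two tailed and a power of 80" percent. The inputs are SD 18 s (assumed equal in the two groups), difference 12 s, two-sided alpha 0.05 and power 0.80. By the normal approximation,

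n per group = 2 (z₀.₉₇₅ + z₀.₈₀)² SD² / difference² = 2 × (1.960 + 0.842)² × 18² / 12² = 35.3, rounded up to 36.

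This reproduces the plan's figure, "a minimum of 36 patients per group should be included in this study". Power is Φ(12 / (18 √(2/n)) − 1.960):

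- n = 36: Φ(2.828 − 1.960) = Φ(0.868) = 80.7%.
- n = 40: Φ(2.981 − 1.960) = Φ(1.021) = 84.6%.

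BMI appears nowhere in these formulas, so either reading of the limit leaves them as they are.

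**4. Does BMI enter the allocation or the analysis?** Randomization describes 40 patients per arm and names no stratification by BMI. Statistical Analysis lists Mann-Whitney, chi-square or Fisher, repeated measures ANOVA and unpaired t-tests, with no BMI covariate or subgroup. Both arms face the same eligibility rule.

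**5. How many patients could sit at exactly 40?** The documents do not say, because they give neither a BMI distribution nor the recording precision. For illustration only, assume that BMI is normal with mean 44 to 48 and SD 5 to 7, and condition on a recorded value of at least 40. The share recorded as exactly 40 is P(lo < BMI < hi) / P(BMI > lo).

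| Recording | lo to hi | Share across the assumed range | Of 80 patients |
|---|---|---|---|
| One decimal | 39.95 to 40.05 | 0.23% to 0.73% | 0.2 to 0.6 |
| Whole number | 39.5 to 40.5 | 2.3% to 7.1% | 1.9 to 5.7 |

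The low ends come from mean 48, SD 5, and the high ends from mean 44, SD 5. These counts are conditional on the assumptions and are not estimates for this trial.

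**The case for a change.** The strongest argument for a correction is that the contradiction is literal, can be checked, and costs one character to remove. The symbols stand in intact sentences, so this is not damage from text extraction. The age pair shows that the authors meant exclusion to mirror inclusion. The document says it follows a reporting standard, and a reader cannot be sure how a patient at 40 was treated. If BMI was kept as whole numbers, several of the 80 could be affected, and no written rule prevents their removal after allocation.

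The inconsistency itself stands, and so does the point that it is cheap to tidy. The consequences drawn from it do not:

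- **Discretion.** Applying the inclusion and exclusion criteria together gives a determinate answer.
- **Removal after randomization.** The documents describe no per-protocol set, no removal of violators and no later eligibility review. BMI was on record the day before surgery, so eligibility could be settled before intubation. Bias would also require removal to depend on arm or outcome, and nothing in the text suggests that.
- **The obvious correction.** Changing the exclusion to below 40 assumes that the inclusion sign is the intended one. The joint reading points the other way, and the documents do not settle it.

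**Conclusion.** No change to the plan follows. The BMI pair is a clerical mismatch confined to one recorded value. Its effect on who enters the trial is limited to patients at exactly 40, whose number is unknown. Its effect on the comparison of the two devices is nil by any route the documents describe: the sample size of 36 per group, the 40 per arm allocation and the planned tests are the same under either reading.

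The conclusion rests on two assumptions. The first is the ordinary convention that a participant must satisfy all inclusion criteria and no exclusion criterion. The second is that no patient was removed after allocation on the ground of BMI, which matches the text, although the text does not state it outright. The document is written in the past tense, so a colleague who wants the point closed need only ask which reading was applied and whether anyone was recorded at 40. That is a matter of reporting and does not alter the design or the analysis.

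### Two unranked primary outcomes with no rule for a positive trial, power stated for time only, and an open choice of test for success that can by itself decide that outcome

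*Combined protocol and SAP*

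**What the plan says.** Outcome Measures names two primary outcomes and ranks neither: "Primary outcome measures were time to intubation and incidence for successful intubations".

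Sample Size addresses only the first. It reads "To show a difference of 12 s between the two groups and with an alpha of 0.05", two-tailed, with 80% power and an SD of 18 s taken from a pilot of 14 patients. It arrives at 36 per group, and 80 patients are enrolled to allow for drop-out. No success rate, target difference or power is given for successful intubation.

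Statistical Analysis applies a single threshold throughout: "Results were evaluated at a 95% confidence interval at a significance level of p < 0.05". For time, "Continuous variables were compared between the groups using a Mann-Whitney U test". For success, the categorical variables "were compared between the groups using a Chi-Square test" or Fisher's exact test, with no statement of when each applies. No section gives a testing order, a multiplicity adjustment or a definition of a positive trial.

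**The concern.** With two primaries and no decision rule, a reader cannot tell which result makes the trial positive. There are two natural readings, and the stated 5% and 80% fail to cover one or the other.

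- **Either primary suffices.** Two chances at 0.05 can take the family-wise error above 5%.
- **Both are required.** Alpha needs no adjustment, but joint power cannot exceed the power for success, for which the trial was not sized.

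The open choice between chi-square and Fisher makes this worse. Where failures are few the two tests can differ widely, so a primary result could turn on a choice made after the table is seen. A non-significant success result could also be taken as evidence that the devices succeed equally often, when the trial may simply be too small to tell.

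**Working it through.** **1. The plan's own figure.** Inputs from Sample Size: difference 12 s, SD 18 s, two-sided alpha 0.05, power 80%.

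n = 2 × (1.96 + 0.842)² × 18² / 12² = 35.3, so 36 per group. This reproduces. At 40 per group, power for time is 84.6% (normal approximation), 83.8% (t-test) and about 81.5% for the planned Mann-Whitney test (simulated, normal data).

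**2. Power for success.** Randomization gives 40 per group. The documents give no success rate, so all rates below are assumptions. Power is the sum, over all pairs of outcomes of two Binomial(40) arms, of the probability of each pair that gives two-sided p < 0.05. The lower rate was reduced until power reached 80%.

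| Better arm | Fisher: other arm (gap) | Uncorrected chi-square, always used: other arm (gap) |
|---|---|---|
| 100% | 81.0% (19.1 points) | 86.6% (13.4) |
| 98% | 76.3% (21.7) | 81.0% (17.1) |
| 95% | 70.7% (24.3) | 73.8% (21.3) |

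For smaller gaps, power is:
- 95% against 85%: about 18% (Fisher) or 35% (chi-square)
- 100% against 90%: about 21% (Fisher) or 58% (chi-square)

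If both primaries are required, joint power is at most the smaller of the two separate powers, however the outcomes are linked.

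**3. Choice of test.** Take 40/40 against 36/40 as an illustration.
- Chi-square: pooled rate 76/80 = 0.95; z = 0.10 / √(0.95 × 0.05 × 2/40) = 0.10 / 0.0487 = 2.05; p = 0.040.
- Fisher: all four failures fall in one arm, so p = 2 × C(40,4)/C(80,4) = 2 × 91,390/1,581,580 = 0.116.

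The same data give opposite conclusions at 0.05, and the plan permits both tests.

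**4. Family-wise error if either primary suffices.** Take time at 0.05 and write s for the exact size of the success test. Under independence the rate is 1 − 0.95 × (1 − s). Under any dependence it is at most 0.05 + s.

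- Fisher, common success 98%: s = 0.0001, giving 5.0%
- Fisher, 95%: s = 0.0040, giving 5.4%
- Fisher, 80%: s = 0.0282, giving 7.7%
- Unrestricted chi-square, 98%: s = 0.0074, giving 5.7%
- Unrestricted chi-square, near 91% (its peak between 98% and 80%): s = 0.0590, giving 10.6%

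The two outcomes are linked, since time ends at successful placement, so the independence figures are approximations. For unrestricted chi-square the bound under any dependence is 0.05 + 0.059 = 10.9%, over the same range of success rates.

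**5. What a null success result would mean.** With 40/40 against 38/40 (again an illustration), Fisher p = 0.49 and the Newcombe 95% CI for the difference runs from −4.5 to +16.5 points.

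**The case against.** The strongest reply is that the alpha problem is minor in practice. The operator was experienced with both devices, so success may well be high in both arms. With Fisher at a common success of 95% to 98%, family-wise error is only 5.0% to 5.4%. That stands for Fisher. It does not settle the matter, because the plan does not commit to Fisher and unrestricted chi-square can pass 10%.

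A second reply is that the size of the power gap depends on the test. This also stands. A reader might take 19 to 24 points as a property of the plan, but that range belongs to Fisher; the plan equally permits a test needing about 13 to 21. Fisher is the sounder choice with few failures, but the plan does not name it for this outcome.

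Third, no equivalence claim is planned, and the sample size is framed around showing a difference. That is correct. Misreading a null result is a risk in reporting, not something the documents propose.

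Fourth, a testing order may come too late. The Protocol section and Statistical Analysis are in the past tense, and the latter reports observed non-normality. The date 27.06.2018, printed after Sample Size, precedes the 8 September 2018 start, but the documents do not say what it refers to. If data were seen, a time-first order controls nothing.

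**Conclusion.** The point holds in limited form. The plan has two primaries without a decision rule, its 80% power covers time only, and the test for success is left open. The sample size for time is sound.

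On assumed rates of 100% to 95% in the better arm, success reaches 80% power only for gaps of about 13 to 24 points, depending on the test. Family-wise error, if either primary suffices, ranges from barely above 5% to about 10.6% under independence for common success of 98% to 80%.

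Two stronger readings are tempting and not supported. One is that the false-positive rate is doubled: this depends on the test and on a success rate the documents do not give, and with Fisher at high success the excess is slight. The other is that 10% is a firm upper limit: unrestricted chi-square exceeds its nominal size at some rates, so its bound is about 10.9%.

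The missing attempt limit for success and the undefined time for a failed intubation are separate points and are not relied on here. This should be fixed, but it does not undermine the design for time.

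**What to change.** In Outcome Measures and Statistical Analysis, state that:

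- time to intubation is tested first at two-sided 0.05, and success at 0.05 only if time is significant;
- success is tested by Fisher's exact test;
- the 80% power applies to time only;
- the success risk difference is reported with a 95% CI, and a non-significant result is read as imprecise, not as equivalence.

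If data are unseen, prespecify this; the order then holds family-wise error at 5% however the outcomes are linked. If data have been seen, report both primaries and disclose the order and the test as post hoc, because the order then does not control alpha.

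The cost is a few sentences and no extra patients; 36 per group stands. The downside is that success loses a stand-alone confirmatory claim, and its power does not improve. A Bonferroni split at 0.025 would also be valid if prespecified, but time would then need 43 per group, and its power at 40 would be 77.0% (normal approximation).

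### Does the silence on repeated or failed intubations leave the two primary outcomes open to conflicting results?

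*Combined protocol and SAP*

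**What the plan says.** Outcome Measures names two primary outcomes: "Primary outcome measures were time to intubation and incidence for successful intubations". The clock is defined at both ends. It starts at pick-up ("Time to intubation was defined as the time from when the anesthesiologist picked up the videolaryngoscope") and runs "to when the anesthesiologist successfully placed the endotracheal tube through the vocal cords", with capnography as confirmation. No device, attempt limit or restart is mentioned.

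Success has no definition of its own. Failure appears only in the secondary ease-of-intubation scale, whose top grade is "3 = failed intubation on first two attempts". The operator records "Incidence, attempts and position for successful intubation", together with the ease grade.

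Under Statistical Analysis, "Continuous variables were compared between the groups using a Mann-Whitney U test", categorical variables are compared by chi-square or Fisher's exact test, and "Quantitative data are presented as mean or standard deviation". No analysis set is described in the visible text; the flow diagram cited under Randomization is not shown in the copy reviewed. Sample Size says: "We ultimately included a total of 80 patients to allow for patient drop-out".

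**The concern.** A trial comparing intubation devices has to decide what to do with the patient who is hard to intubate. If such patients can be kept in or left out of the time analysis, and counted as successes or failures, the choice may be made with the data in hand. Leaving out the slowest patients of one arm flatters that arm. Counting any eventual success can turn a visible difference in success into 100% v 100%. Both primary outcomes are touched, and the person recording success knows which device was used. It is also not said whether a failed intubation counts towards the drop-out allowance.

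**Working it through.** **1. The plan's own figure.** Inputs from Sample Size: SD 18 s, difference 12 s, two-sided alpha 0.05, power 80%.

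n per group = 2 × (1.960 + 0.842)² × 18² / 12² = 2 × 7.85 × 2.25 = 35.3, so 36, as stated. With 40 per group, z = 12 / (18 × √(2/40)) − 1.96 = 2.98 − 1.96 = 1.02, which is a power of about 85%. The allowance is 40 − 36 = 4 patients per arm.

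**2. What the written definitions give each type of patient.**

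| Patient | Time | Success, any attempt | Success, first attempt |
|---|---|---|---|
| Intubated at first attempt | yes | yes | yes |
| Intubated at second attempt | yes, longer | yes | no |
| Ease grade 3, intubated later | yes, longer still | yes | no |
| Never intubated | none | no | no |

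Only the last row lacks a time, and that patient is a failure on both readings of success. The third row is the open one: its time is defined, but its success status depends on the reading. Because attempts are listed separately from incidence, success at any attempt is the more natural reading, though it is not explicit.

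**3. Success counted both ways.** The documents give no failure rate, so k ease-grade-3 patients in one arm and none in the other is an assumption. With 40 per arm, two-sided Fisher p = 2 × C(40,k) / C(80,k):

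- k = 2: 2 × 780 / 3,160 = 0.49 (95% v 100%)
- k = 4: 2 × 91,390 / 1,581,580 = 0.12 (90% v 100%)
- k = 5: 0.055 (87.5% v 100%)
- k = 6: 0.026 (85% v 100%)

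If any eventual success counts, each of these becomes 100% v 100%. The two readings differ at the 0.05 level only from 6 v 0, that is, when 15% of one arm and nobody in the other fail twice.

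**4. Time, if someone departed from the definition and left these patients out.** Assumed: k patients with kept times uniform on 90 to 180 s (average 135 s); the rest of the arm has a mean of 45 s, or 57 s if it is the slower arm. The mean kept minus left out is k × (135 − m) / 40:

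- k = 1: 1.95 s (m = 57) to 2.25 s (m = 45)
- k = 2: 3.9 to 4.5 s
- k = 4: 7.8 to 9.0 s

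If the slowest patients are the ones removed, the upper ends rise to 2.3, 4.6 and 9.4 s. A single patient moves the mean by (90 − 57)/40 = 0.8 s to (180 − 45)/40 = 3.4 s. These are descriptive shifts; the planned test uses ranks.

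For the Mann-Whitney test, simulation (20,000 trials per scenario, 40 per arm, normal or log-normal times, SD 18 s) gave the following for 1 / 2 / 4 failures in one arm:

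- Equal true times, slowest patients left out: rejection 5.5–6.1 / 6.9–7.2 / 12.4–12.9%.
- Equal true times, failures unrelated to speed, left out: about 5% throughout.
- Kept and left-out verdicts differ in 2–7 / 4–16 / 8–38% of trials. The 38% needs 4 v 0 failures, unrelated to speed, in an arm truly 12 s faster.
- With 1 v 1 or 2 v 2 failures, the verdict differs in 1–5% of trials.

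**5. Would a stricter rule do better?** Giving failures the worst rank rejects in about 10% of trials when true times are equal and 4 v 0 failures are unrelated to speed. It mixes speed with success, which is already the other primary outcome. It could serve as a sensitivity analysis but is not a better primary method.

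**The case for a change.** The strongest case for acting is the success outcome. It is primary and undefined, it is recorded by an unblinded operator, and the plan itself foresees failure after two attempts. No inference about rescue is needed: a patient intubated at the third attempt with the allocated device can be counted either way, and both counts fit the text. A few sentences would settle it. Means are also among the figures to be reported, and a few long times move them by an amount that is not trivial beside 12 s.

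The gap in wording stands, as does the absence of a rule for a patient never intubated. The consequence is weaker. Attempts and ease grade are recorded, and as categorical variables they are summarised and compared under the same section, so repeat failures cannot disappear from the report. The time figures rest on leaving patients out, which no passage provides for. No passage mentions rescue or another device either, and the recorded items do not include the device that achieved intubation, so a rule based on it would need data the plan does not list. General Anesthesia Protocol requires an operator with more than 200 successful uses of both devices, which makes several double failures in one arm less likely.

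**Conclusion.** The plan leaves a detail unstated, and no change follows. Time to intubation, applied as written with one interval from first pick-up to final placement and patients kept in their allocated arm, gives a sound result for everyone eventually intubated. Anyone never intubated is a failure on the success outcome. For success, an analyst can report first-attempt and overall rates from the recorded attempts, with ease grade beside them, and the ambiguity has no effect.

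The size depends on a failure count that the documents do not give. It is nil with no failures. With 2 v 0 ease-grade-3 patients, neither way of counting success approaches significance. The two counts disagree at 0.05 only from 6 v 0. The larger effects on time need both a departure from the written definition and several failures confined to one arm, with assumed kept times of 90 to 180 s. Worst-rank scoring brings its own distortion, so there is no clearly better primary analysis to move to.
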